AR _{C_{max}}	Accumulation ratio for C _{max}
AR _{AUC}	Accumulation ratio for AUC
AUC _{inf}	Area under the concentration curve from t ₀ to infinite time
AUC _{last}	Area under the concentration curve from dosing to the time of the last measured concentration
AUC _t	Area under the plasma concentration-time curve from time zero to the end of the dosing interval
AST	Aspartate aminotransferase
BID	Twice daily
BMI	Body mass index
BP	Blood pressure
BSAP	Bone specific alkaline phosphatase
CFR	Code of Federal Regulations
C _{max}	Maximum concentration
COVID-19	Coronavirus disease 2019
CRA	Clinical research associate
CRU	Clinical Research Unit
CTCAE	Common Terminology Criteria for Adverse Events
CTD	Common Technical Document
CTX	Collagen Type- C-Telopeptide
CYP3A4	Cytochrome P450 3A4
CYP2D6	Cytochrome P450 2D6
ECG	Electrocardiogram
eCRF	Electronic case report form
EDC	Electronic data capture
EOS	End of study
ET	Early termination
FDA	Food and Drug Administration
FSH	Follicle stimulating hormone
GCP	Good Clinical Practice
GFR	Glomerular filtration rate
HbsAg	Hepatitis B surface antigen
HCV	Hepatitis C virus
HEENT	Head, eyes, ears, nose, and throat
HIV	Human immunodeficiency virus
HRT	Hormone replacement therapy
IB	Investigator's Brochure

Abbreviation	Description
ICF	Informed consent form
ICH	International Conference on Harmonization
ICMJE	International Committee of Medical Journal Editors
IRB	Institutional review board
iVMS	Induced vasomotor symptoms
LH	luteinizing hormone
MDRD	Modification of diet in renal disease
MedDRA	Medical Dictionary for Regulatory Activities
MITT	Modified Intent-to-Treat Population
MR _{C_{max}}	Metabolite:parent ratio of C _{max}
MR _{AUC}	Metabolite:parent ratio of AUC
NCA	Noncompartmental analysis
NKA	Neurokinin A
NKB	Neurokinin B
NK	Neurokinin
NK3R	Neurokinin 3receptor
NTA	Night-time awakenings
OTC	Over the counter
P1NP	Amino terminal propeptides of type 1 collagen
PK	pharmacokinetic(s)
QD	Once daily
SAE	Serious adverse event
SAP	Statistical analysis plan
SHBG	Sex hormone binding globulin
SNRI	Serotonin and norepinephrine reuptake inhibitors
SOP	Standard operating procedure
SP	Substance-P
SSRI	Selective serotonin reuptake inhibitor
SUSAR	Suspected unexpected serious adverse reaction
TEAE	Treatment-emergent adverse event
T _{max}	Time to reach maximum concentration
TSH	Thyroid-stimulating hormone
ULN	Upper limit of normal
US	United States
VMS	Vasomotor symptoms
WHODDrug	World Health Organization Drug Dictionary

2 INTRODUCTION

Acer acquired the rights to osanetant (SR142801), a selective non-peptide neurokinin 3 receptor (NK3R) antagonist, from Sanofi on December 2018 and has since renamed the compound ACER-801. ACER-801 is being investigated for the prevention/treatment of moderate/severe vasomotor symptoms (VMS) in patients with medically or surgically induced VMS (iVMS).

The efficacy and safety of ACER-801 in subjects with iVMS has not been evaluated to date. Osanetant (SR142801) has been studied in a total of 23 completed clinical studies conducted by Sanofi with osanetant doses ranging from 5 mg to 1000 mg in healthy subjects and 50 mg to 200 mg once daily (QD) in patients with schizophrenia, major depressive disorder, Parkinson's disease, panic disorder, and asthma. In these studies, osanetant was found to be well tolerated, with minimal safety issues.

2.1 Background

Neurokinin B (NKB) belongs to a group of neuropeptides, called tachykinins or neurokinins (Nks), that includes substance-P (SP), and neurokinin A (NKA). The biological effects of tachykinins are mediated through specific receptors denoted NK1, NK2, and NK3. NKB is the preferred endogenous ligand of tachykinin NK3 receptors. The tachykinin NK3 receptors (NK3R) are located primarily in the brain, while a few receptors are also present in the peripheral nervous system. The NK receptor pathway in the hypothalamus, including NK3, has been shown to play a role in the etiology of VMS ([Prague 2017](#); [Skorupskaite, 2018](#)).

VMS are generally defined as hot flashes, flushing and night sweats that most often occur in women entering or in menopause. VMS are causally related to decreased estradiol concentrations mainly in the systemic circulation and subsequently also in the hypothalamic temperature regulating center. The lack of estrogens alters neurotransmitter activity, especially in the serotonergic and noradrenergic pathways. Because sex steroids act as potent neuromodulators, the substitution of ovarian steroids by hormone replacement therapy (HRT) is currently the most effective treatment option for VMS.

Clinical studies with a dual NK1/NK3 antagonist (NT-814) and selective NK3 antagonists (fezolinetant and MLE4901 [pavinetant]) in menopausal women significantly reduced VMS ([Trower, 2020](#); [Fraser, 2020](#); [Santoro, 2020](#), Prague, 2017). Based on the demonstrated role of the NK pathway in the etiology of VMS, it is hypothesized that administration of the NK3 receptor antagonist, ACER-801, will result in similar findings by modulating the NKB pathway directly.

While VMS associated with menopause can often be treated with HRT, there are subjects who experience VMS who are not in menopause and in whom HRT is not the preferred or acceptable treatment. VMS can be induced (iVMS) with the use of hormonal cancer therapies and certain surgical procedures. Under these situations, VMS can appear immediately and be severe and, in many instances, HRT therapy is not the preferred treatment.

ACER-801 may be a novel, non-hormonal, centrally acting therapy for iVMS.

2.2 Safety Data

To date, no studies have been conducted with ACER-801 in subjects with iVMS.

Safety data are summarized for completed clinical studies conducted with osanetant by Sanofi. These studies were conducted in healthy subjects and patients with schizophrenia, major depressive disorder, Parkinson's disease, panic disorder, and asthma.

Osanetant was evaluated in 23 completed Phase 1 and Phase 2 studies. In single- and repeat-dose Phase 1 studies, approximately 400 subjects were exposed to doses ranging from 5 mg to 1000 mg in single dose studies and from 5 mg to 1000 mg (500 mg twice daily [BID]) in repeat-dose studies in which subjects received osanetant for up to 21 days.

In the 7 completed Phase 2 studies, a total of 821 patients were exposed to osanetant, including patients with depression (up to 200 mg QD for 6 weeks), patients with panic disorder (200 mg QD for 4 weeks), patients with schizophrenia (200 mg QD for 16 weeks), patients with asthma (200 mg QD for 6 weeks), and patients with Parkinson's disease (100 or 200 mg QD for 9 days).

Data from these studies demonstrated no major safety concerns after single-dose and repeat-dose administration up to 400 mg QD in healthy subjects, and 200 mg QD in the patient population. In controlled clinical trials, there is no evidence to date for liver function test abnormalities or weight loss, as noted in the toxicology studies.

The incidence of adverse events (AEs) was similar in the osanetant and placebo groups in completed Phase 1 and 2 trials. In patients, the serious adverse events (SAEs) reported in the osanetant group were mainly related to the condition being treated. Adverse events most frequently reported in osanetant-treated patients were headache, nausea, dyspepsia, insomnia, dizziness, and abdominal pain. These incidences were comparable in the osanetant and placebo groups.

Additional details can be found in the Investigator's Brochure.

2.3 Rationale for Study Design and Dose for Investigational Product

A 200 mg BID dose was chosen as the maximum dose based on previous studies in healthy subjects where a 400 mg QD dose up to 21 days was shown to be safe. The subjects in this study will be healthy with no outstanding medical issues who present with moderate to severe VMS.

3 STUDY OBJECTIVES AND PURPOSE

3.1 Primary Objective

The primary objectives are to:

- Evaluate the pharmacokinetic (PK) profile of ACER-801 and its metabolite at different doses
- Evaluate the safety profile of ACER-801 at different doses

3.2 Secondary Objectives

The secondary objectives are to:

- Evaluate the effect of ACER-801 at different doses on the frequency of vasomotor symptoms associated with menopause compared to placebo
- Evaluate the effect of ACER-801 at different doses on the severity of vasomotor symptoms associated with menopause compared to placebo
- Evaluate the effect of ACER-801 at different doses on the hot flash severity score compared to placebo

3.3 Exploratory Objectives

The exploratory objectives are to evaluate:

- The effect of ACER-801 at different doses on change in hormones compared to placebo including:
 - luteinizing hormone (LH)
 - follicle stimulating hormone (FSH)
 - estradiol
 - testosterone
 - sex hormone binding globulin (SHBG)
 - adrenocorticotropic hormone (ACTH)
 - cortisol
 - thyroid-stimulating hormone (TSH)
 - Triiodothyronine (T3) (Total and Free)
 - Thyroxine (T4) (Total and Free)
- Changes in the number night-time awakenings (NTA)
- Change in blood bone density marker concentration
- Changes in blood markers associated with stress
- Change in electrocardiogram (ECG) variables (heart rate, RR, PR, QRS, QT, QTcF, and QTcB)
- The relationship between PK exposure and measures of efficacy and/or safety

4 INVESTIGATIONAL PLAN

4.1 Overall Study Design

This is a Phase 2a, randomized, double-blind, placebo-controlled, dose-ranging study in post-menopausal women in which the pharmacokinetic (PK) profile of ACER-801 at different doses is evaluated and the efficacy of ACER-801 (50 mg twice daily [BID], 100 mg BID, and 200 mg BID) will be compared to placebo in approximately 40 to 56 subjects (approximately 10 to 14 subjects per treatment arm).

Subjects will enter a Screening Period to determine eligibility. Subjects will be required to complete hot flash diaries for 2 weeks prior to randomization. Eligible subjects will be admitted to a Clinical Research Unit (CRU) on Day -1 and remain in the clinic from Day -1 until discharge on Day 16 after completion of treatment and all study assessments or upon withdrawal from the study. The study includes a 14-day safety follow-up assessment (Day 28) ([Figure 1](#)).

Subjects will be randomized in a 1:1:1:1 ratio to ACER-801 per one of the following dosing schedules prior to dosing:

- 50 mg BID
- 100 mg BID,
- 200 mg BID, or
- placebo administered orally for 14 consecutive days (28 doses).

[figure not shown]
Blood samples for PK (plasma) assessment will be collected for concentrations of ACER-801 and its metabolite at predose, 0.5, 1.0, 1.5, 2.0, 2.5, 3.0, 4.0, 5.0, 6.0, 8.0, 12.0 (prior to evening dose), and 15.0 hrs post morning dose on Day 1 and Day 14, as well as predose (prior to morning dose) on Day 2 and Day 7. Plasma samples will also be collected 24 hrs (Day 15) and 48 hrs (Day 16) after the morning dose on Day 14.

Throughout the duration of the study (Day 1 through Day 16), subjects will be required to record the frequency and severity of hot flashes in a subject diary (continuous hot flash diary).

Electrocardiographs using the Mortara Surveyor will be collected on Day -1, Day 1, and Day 14.

During the study, subjects will be closely monitored for safety including assessments of AEs, 12-lead ECGs, atrial oxygen saturation using pulse oximetry, vital signs (sitting and standing blood pressure (BP), heart rate, oral body temperature, and respiratory rate), clinical labs, and physical examinations.

Figure 1 Study Design of ACER-801-201

An overview of the study procedures is presented in Study Duration

This study consists of a 28-day Screening Period, a 14-day Treatment Period, and a 14-day Safety Follow-Up Period.

4.2 Number of Subjects and Target Population

Approximately 40 to 56 post-menopausal women aged 40-65, inclusive, who experience an average of 10 to 20 moderate to severe hot flashes per day as determined by a continuous hot flash diary where events are recorded for 2 weeks prior to randomization will be included in this study. Subjects will have no active, ongoing health conditions that could cause difficulty in interpretation of hot flashes categorized as moderate to severe.

4.3 Treatment Assignment

Subjects will be randomly assigned in a blinded manner to 1 of 4 treatment arms (placebo or 50 mg BID, 100 mg BID, or 200 mg BID ACER-801).

Table 1 Schedule of Study Procedures

Activity	Screening Visit	In Clinic									EOS
		PK Days			PK Day			PK Days			
	Day -28 to Day -1 ¹³	Day -1 ²	Day 1 ²	Day 2	Day 3 -Day 6	Day 7	Day 8- Day 13	Day 14/ EOT	Day 15	Day 16/ ET ¹¹	
Informed consent ¹	X										
Eligibility criteria review	X	X ²									
Fasting ³	X	X	X	X		X		X		X	
Admission		X									
COVID-19 test		X									
Medical history	X	X									
Concomitant medication review							Continuous Collection				
Physical exam	X		X							X	
Vital signs ⁴	X	X	X	X	X	X	X	X	X	X	
Weight	X	X									X
Height	X										
Serum pregnancy testing			X								
Standard Urine drug Screen	X	X									
Virology (HIV antibody, HBsAg, and HCV)	X										
FSH (for eligibility)	X										
Randomization ⁵			X	X							
12-lead ECG for Safety ¹⁶	X	X	X							X	
Electrocardiographs using the Mortara Surveyor ¹⁵		X	X					X			
Blood bone density marker concentration			X					X			
Biochemistry/ Hematology, Coagulation ¹⁴	X	X	X			X		X		X	
Provide instructions on recording of hot flashes ⁶	X										
Continuous hot flash diary ⁶	X	X	X	X	X	X	X	X	X	X	
Record bedtime and morning wake-up time in hot flash diary ⁶	X					Continuous Collection					
Catecholamines, vasopressin, gonadotropins, prolactin, insulin ¹⁴			X					X		X	
SHBG, estradiol, testosterone, ACTH, cortisol, TSH, total and free T3 and total and free T4, FSH ¹⁴			X					X			
Urinalysis ¹⁴	X	X				X		X		X	
LH ^{7, 10}		X	X	X	X			X			

Table 1 Schedule of Study Procedures

Activity	Screening Visit	In Clinic									EOS
		PK Days			PK Day			PK Days			
Day -28 to Day -1 ¹³	Day -1 ²	Day 1 ²	Day 2	Day 3 -Day 6	Day 7	Day 8- Day 13	Day 14/ EOT	Day 15	Day 16/ ET ¹¹		
Dosing ⁸			X	X	X	X	X				
PK ^{9, 10}			X	X		X		X	X	X	
Discharge										X	
AE collection		Continuous AE Collection									

AE=adverse event; ACTH=adrenocorticotrophic hormone; CTX = Collagen Type- C-Telopeptide; EOT=end of treatment; ET=early termination; EOS=end of study; FSH=follicle stimulating hormone; LH=luteinizing hormone; PK=pharmacokinetics; SHBG=sex hormone binding globulin; TSH=thyroid stimulating hormone; T3=triiodothyronine; T4=thyroxine.

¹Informed consent must be signed by the subject before the start of any study procedure.

²Key inclusion/exclusion criteria must be re-assessed before conducting any other baseline assessments. All baseline assessments to be conducted on Day -1 (and/or Day 1 as indicated) to be conducted prior to dosing unless otherwise indicated (See [Section 7](#)).

³Subjects will be required to fast for approximately 8 hours prior to their Screening Visit and Day 16. Subjects will be required to fast for 12 hours prior collection of laboratory sample for CTX on Day 1 and Day 14. CTX blood sample must be collected prior to dosing. Subjects will be required to fast for 4 hours post morning dose on Day 1 and Day 14. Subjects will also be required to fast for 8 hours prior to Day -1 and from midnight prior to dosing (approximately 8 hours) Day 2 and Day 7. Water will be allowed *ad libitum*.

⁴Vital signs, including oral body temperature, pulse oximetry, respiratory rate, and sitting and standing BP and heart rate, will be performed daily during the study period approximately 60 minutes prior to am dosing. The minimal positional time for collection of the orthostatic vital signs is approximately 5 minutes sitting and approximately 2 minutes standing prior to collection of vital signs.

⁵Randomization can occur on Day -1 or Day 1 but must occur before dosing.

⁶Continuous hot flash diary: Instructions on the use of the continuous hot flash diary will be provided at Screening. Subjects are required to record the frequency and severity of the hot flash (scale 1 to 3) in a continuous hot flash diary for 2 weeks prior to randomization (during the day and at night). Subjects will record the frequency and severity of hot flash while in the clinic Day -1 to Day 16 (during the day and the night). Subjects are also to record the time they went to sleep, and morning wake up time.

⁷Luteinizing hormone (LH) sampling on Day-1 and predose and every 60 mins starting at 60 minutes after dose 0 to 8 hrs Day 1, Day 2, and Day 14.

⁸Study drug will be administered twice daily, approximately 12 hours apart (morning and evening dose) from Day 1 through Day 14. All applicable study procedures must be completed prior to administration of the morning study drug. Subjects will be required to fast for 12 hours prior to study drug administration and for 4 hours post morning dose on Days 1 and 14. Subjects will be required to fast for 8 hours prior to morning study drug administration on Days 2 and 7. No fasting is required on Days 3 – 6 or Days 8 – 13.

⁹PK Sampling at predose, 0.5, 1.0, 1.5, 2.0, 2.5, 3.0, 4.0, 5.0, 6.0, 8.0, 12.0 (prior to evening dose) and 15.0 hours post morning dose on Day 1 and Day 14, as well as predose (morning) on Day 2 and Day 7. Plasma samples will also be collected 24 hours (Day 15) and 48 hours (Day 16) after the morning dose on Day 14.

¹⁰Predose samples for PK and LH to be taken within 30 minutes prior to dose administration.

¹¹Where possible, all subjects who are withdrawn or withdrawn from the study early will undergo the Early Termination Visit assessments.

¹²14-Day Safety Follow-up Visit; subjects will be contacted by telephone 14 days (± 4 days) following the final dose of study drug on Day 14, unless deemed by the investigator that a clinic visit is more appropriate to follow up an adverse event.

¹³If the Screening Period is >28 days the following procedures must be repeated such that the most recent evaluation occurs within 28 days of their scheduled randomization: biochemistry, hematology, coagulation, vital signs, 12-lead ECG, physical examination. If the subject has completed (or partially completed) the continuous Hot Flash Diary this must still be repeated, and a new continuous hot flash diary started on the new planned Day -15 and completed for the 2 weeks up to Day -2. Eligibility will be assessed on the repeated continuous hot flash diary, not the initial one. If the subject had not started completing their screening continuous hot flash diary at the time screening was put on hold, they will start this screening continuous hot flash diary on the re-scheduled Day -15.

¹⁴To be collected predose on dosing days.

¹⁵Time and duration of Mortara Surveyor ECG collection must be identical on Day -1, Day 1, and Day 14 and must be planned in relation to predose and 15 hrs postdose PK time points.

¹⁶The safety ECG readings will be performed approximately 1 hour after the scheduled morning dose on dosing days.

5 SELECTION AND WITHDRAWAL OF SUBJECTS

5.1 Inclusion Criteria

To be eligible to participate in this study, subjects must meet all the following criteria:

1. Post-menopausal female subjects 40-65 years of age, inclusive.
Menopause will be defined as:
 - a. At least 12 months of spontaneous, continuous amenorrhea, or
 - b. At least 6 months of spontaneous, continuous amenorrhea with serum FSH levels > 40 mIU/mL at screening, or
 - c. At least 6 weeks postsurgical bilateral oophorectomy with or without hysterectomy.
2. At baseline women:
 - a. With an average of ≥ 7 and ≤ 20 moderate to severe hot flashes/day for 2 weeks prior to randomization (per continuous hot flash diary) ([Sloan, 2012](#)). The minimum number of hot flashes on each day during the 2 weeks prior to randomization must be at least 7.
 - b. That have a change of $< 50\%$ in average 24-hour hot flash frequency 2 weeks prior to randomization.
 - Moderate: defined as sensation of heat with sweating, able to continue activity.
 - Severe: defined as sensation of heat with sweating, causing cessation of activity.
3. Able to understand and comply with the requirements of the study and sign Informed Consent forms.
4. Have not participated in any clinical research study evaluating another investigational drug, device or therapy within 30 days or within 5 half-lives (whichever is longer), of the investigational drug prior to consenting to study entry.

5.2 Exclusion Criteria

To be eligible to participate in this study, subjects must not meet any of the following criteria:

1. Any active comorbid disease deemed by the investigator to be clinically significant, which could impact safety during study conduct including renal or hepatic impairment:
 - a. Serum creatinine laboratory value greater than 1.2 times upper limit of normal (ULN) reference range (after adjustment for age) at Screening or Day -1 or subjects with renal function glomerular filtration rate (GFR) <60 mL/min/1.73m² based on the Chronic Kidney Disease Epidemiology Collaboration (CKD-EPI) equation.
 - b. Total bilirubin greater than upper limit of normal reference range (with the exception of Gilbert's Syndrome) and/or alanine aminotransferase (ALT) >2 times ULN reference ranges and/or aspartate aminotransferase (AST) >2 times ULN reference ranges at Screening or Day -1.
Laboratory values may be repeated once to confirm results.
2. Any active medicinal (pharmaceutical or homeopathic) therapy considered by the investigator to potentially cause hepatic impairment leading to elevated:
 - c. ALT and/or AST ranges.

3. Subjects with a prior medical history of or an increased risk of seizures, or who have a history of recent (within 6 months of Screening) head trauma that resulted in a loss of consciousness or concussion.
4. Any prior or ongoing history of arrhythmias.
5. Any ongoing cardiovascular disease including heart failure, coronary artery disease, or uncontrolled hypertension or uncontrolled diabetes (blood sugar level consistently over 100 mg/dL while fasting, higher than 180 mg/dL two hours after a meal, or random blood glucose levels higher than 200 mg/dL). Postmenopausal women with a history of hypertension must be medically cleared to participate in the study. Hypertension is defined as systolic blood pressure ≥ 130 mg Hg or diastolic blood pressure ≥ 80 mg over 3 readings on at least 2 different occasions, unless the participant receives medical clearance by her physician to participate in the trial.
6. Any clinically relevant ECG abnormalities at Screening, per Investigator discretion.
7. Use of any prohibited medications (see [Section 5.3.2](#)).
8. Any history of malignancy in the past 2 years.
9. Any active ongoing condition that could cause difficulty in interpreting vasomotor symptoms such as: infection that could cause pyrexia, pheochromocytoma, hypothyroidism, hyperthyroidism, carcinoid syndrome, alcohol abuse.
10. Body mass index (BMI) >35 kg/m².
11. Inability to complete questionnaires or continuous hot flash diary for any reason including psychiatric disorders and inability or unwillingness to use electronic devices.
12. History of hypothalamic dysfunction.
13. Any clinically significant or unstable medical or psychiatric condition that would interfere with the subject's ability to participate in the study including anxiety syndromes.
14. Any clinically significant abnormal laboratory test result(s) measured at Screening or on Day -1.
15. Participation in any clinical research study evaluating another investigational drug, device, or therapy within 30 days or within 5 half-lives (whichever is longer), of the investigational drug prior to consenting to study entry. If the subject is in an observational clinical study, no washout is required.
16. Subjects who, in the opinion of the investigator, should not participate in the study for any other reason.
17. Any known allergy or hypersensitivity to any of the ingredients in the study medication or to skin adhesives.
18. Current or planned use of other agents for treating hot flashes.
19. History or presence of alcohol abuse (defined as consumption of more than 210 mL alcohol per week, or the equivalent of fourteen 4 ounce glasses of wine or fourteen 12 ounce cans/bottles of beer or wine coolers per week) within 6 months before Screening or positive alcohol test at Screening or Check in (Day -1).
20. History or presence of substance abuse within the past 2 years or positive drug screen test at Screening or Check in (Day -1).
21. Presence of hepatitis B virus, hepatitis C virus (HCV), or human immunodeficiency virus (HIV) at Screening.
22. Current use or has used tobacco-or nicotine-containing products (e.g., cigarettes, cigars, chewing tobacco, snuff, vaping) within 30 days prior to first dose.
23. Known or suspected pregnancy on Day -1.

24. Positive COVID-19 test on Day -1.

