7.1 Screening Procedures (Day -28 to Day -1)

Within 28 days of Day -1, after subjects have provided a signed voluntary written ICF, subjects will be screened for enrollment into the study. The following study evaluations will be performed at screening:

- Written informed consent
- Inclusion/exclusion criteria
- Document fasting period (minimum of 8 hours)
- Concomitant medication review
- Medical history and demographic data
- Urine drug screen
- Virology testing
- Physical examination
- Vital signs
- Weight
- Height (determine BMI for eligibility)
- 12-lead ECG (for safety)
- Biochemistry, Hematology, and coagulation
- Urinalysis
- FSH for eligibility
- Instructions for continuous hot flash diary
- Continuous hot flash diary reporting for 2 weeks prior to randomization (including hot flashes during the day and night)
- Daily recording of bedtime and morning wake up time for 2 weeks prior to randomization.
- AE monitoring (after the ICF has been signed)

The screening visit assessments must be performed within 28 days prior to Day -1 to determine whether the subject meets all the inclusion criteria and none of the exclusion criteria. Subjects who do not fulfill all eligibility criteria will not be enrolled in the study.

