7.2 Check-In Procedures (Day -1)

The AE reporting period will begin at the time of the signing of the ICF and continues through the Follow-up phone call.

Subjects will be admitted to the CRU where they will reside from Day -1 to Day 16. All study procedures, including study drug administration, will occur in the CRU. On Day -1, the following procedures will be performed:

- Check-in to clinical unit (start of confinement in clinical unit)
- Confirmation of inclusion/exclusion criteria
- Collect continuous hot flash diary information to confirm eligibility
- Document fasting period (minimum of 8 hours)
- Concomitant medication review
- Medical history
- COVID-19 test
- Vital signs
- Weight
- 12-lead ECG (for safety)
- Urine drug screen
- Serum pregnancy testing
- Electrocardiographs using the Mortara Surveyor (time and duration of ECG collection must be identical on Day -1, Day 1, and Day 14 and must be planned in relation to predose and 15 hrs postdose PK time points)
- Daily recording of bedtime and morning wake up time.
- Biochemistry, hematology, and coagulation
- Continuous hot flash diary reporting (including hot flashes during the day and night)
- LH
- Urinalysis
- AE monitoring
- Randomization can occur on Day -1 or Day 1 (prior to dosing)

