7.4 Day 1 (Confined to CRU)

In addition to study procedures outlined in Section 7.3, all study procedures must be performed prior to morning study administration unless otherwise indicated.

- Document fasting period (minimum of 12 hours) prior to administration of morning study drug and 4 hours after dosing
- Randomization (prior to dosing on Day 1 or Day -1)
- Physical exam

- Electrocardiographs using the Mortara Surveyor (duration and time of collection must be the same on Day -1, Day 1, and Day 14)
- Blood bone density markers
- Biochemistry, hematology, and coagulation
- Catecholamines, vasopressin, gonadotropins, prolactin, insulin collection
- Estradiol, testosterone, SHBG, ACTH, cortisol, TSH, T3 (Total and Free), T4 (Total and Free), FSH collection
- LH assessment
- PK assessment (30 min predose)

Post morning dose:

- 12-lead ECG (for safety) (1-hour post-morning dose)
- PK assessments
- LH assessment (every 60 mins starting at 60 minutes after dose 0 to 8 hrs)

7.5 Day 2

In addition to study procedures outlined in [Section 7.3](#), all study procedures must be performed prior to morning study administration unless otherwise indicated.

- Confirm fasting (8 hours prior to dosing)
- LH assessment
- PK assessment (30 min predose)

Post morning dose:

- LH assessment (every 60 mins starting at 60 minutes after dose 0 to 8 hrs)

7.6 Day 7

In addition to study procedures outlined in Section 7.3, all study procedures must be performed prior to morning study administration unless otherwise indicated.

- Confirm fasting (8 hours prior to dosing)
- Biochemistry, hematology, and coagulation
- Urinalysis
- PK assessment (30 min predose)

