The total amount of blood taken for the entire study will be approximately 508 mL.

Table 5 List of Clinical Laboratory and Other Analytes to be Tested

Assessment	Analyte
Central Laboratory (Clinical Site)	
Hematology	Hemoglobin, hematocrit, white blood count with differential (neutrophils, lymphocytes, monocytes, eosinophils, basophils), platelet count, red blood cell count (including mean corpuscular volume, mean corpuscular hemoglobin, mean corpuscular hemoglobin concentration)
Coagulation	Prothrombin time, partial thromboplastin time, international normalized ratio
Serum chemistry	Albumin, alkaline phosphatase, total bilirubin, ALT, AST, blood urea nitrogen, calcium, carbon dioxide, chloride, potassium, sodium, total cholesterol, creatinine, gamma glutamyl transferase, glucose, lactate dehydrogenase, phosphorus, total protein, uric acid
Virology	HIV antibody types 1 and 2, HCV antibody, HbsAg
Peptides	Neurokinin B
Hormones	Catecholamines, vasopressin, gonadotropins, estradiol, testosterone, FSH, LH, ACTH, cortisol, TSH, T3 (Total and Free), T4 (Total and Free), prolactin, SHBG, and insulin
Bone Density markers	BSAP, osteocalcin, amino terminal propeptide of type 1 collagen (P1NP) and Collagen Type- C-Telopeptide (CTX)
Urinalysis	pH, specific gravity, protein, glucose, ketones, bilirubin
Drugs of abuse, cotinine, and alcohol	Drugs of abuse including cocaine, amphetamines, barbiturates, opiates, benzodiazepines, cannabinoids, methadone, cotinine (nicotine), and alcohol
Pregnancy test	Serum pregnancy test
COVID-19 screen	As per site policy.
PK Laboratory	
PPD	ACER-801, metabolite

Note: Blood samples may also be used for the assessment of tachykinin peptides, including NKB, NKA, and substance P.

Abbreviations: ACTH = adrenocorticotrophic hormone; ALT = alanine aminotransferase; AST = aspartate aminotransferase; BSAP = Bone specific alkaline phosphatase COVID-19 = coronavirus disease 2019; FSH = follicle stimulating hormone; HbsAG = hepatitis B surface antigen; HCV = hepatitis C virus; HIV = human immunodeficiency virus; LH = luteinizing hormone; PK = pharmacokinetic; SHBG = sex hormone binding globulin; TSH = thyroid-stimulating hormone; T3 = triiodothyronine; T4 = thyroxine.

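### Active thyroid disease is an exclusion, but no scheduled eligibility step uses a thyroid test: TSH, T3 and T4 are first drawn on Day 1, after the last eligibility review

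*Combined protocol and SAP*

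**What the plan says.** Exclusion 9 (Section 5.2, repeated in the Synopsis) bars active conditions that would make vasomotor symptoms hard to interpret, and gives as examples "infection that could cause pyrexia, pheochromocytoma, hypothyroidism, hyperthyroidism, carcinoid syndrome, alcohol abuse". It names no thyroid test and no limit.

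The Screening list (Section 7.1) has one hormone, entered as "FSH for eligibility". The Day -1 list (Section 7.2) also has one, LH. The serum chemistry run at both visits is defined in Table 5; it begins "Albumin, alkaline phosphatase, total bilirubin, ALT, AST, blood urea nitrogen, calcium, carbon dioxide, chloride, potassium, sodium, total cholesterol, creatinine" and has no thyroid analyte anywhere in the row. TSH, T3 and T4 sit in Table 5's separate hormone row.

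The thyroid tests first appear in Section 7.4 (Day 1), among the procedures to be done before the morning dose: "Estradiol, testosterone, SHBG, ACTH, cortisol, TSH, T3 (Total and Free), T4 (Total and Free), FSH collection". They recur on Day 14 (Section 7.7). Table 1 has the same row, "SHBG, estradiol, testosterone, ACTH, cortisol, TSH, total and free T3 and total and free T4, FSH", marked on Day 1 and Day 14 only, and footnote 14 makes the draw predose.

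The general laboratory exclusion, number 14, covers "Any clinically significant abnormal laboratory test result(s) measured at Screening or on Day -1". Section 12.5.1 uses the thyroid results for the exploratory summary of hormone change from baseline.

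**The concern.** The protocol judges that thyroid disease would confuse the efficacy measure, and it pays for the assay that would show it. Yet it schedules that assay where no eligibility decision draws on it. A woman with unrecognised thyroid disease can pass Screening and Day -1, be randomized and dosed, and be identified only afterwards.

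She would then count in the modified intent-to-treat set once she has baseline and post-baseline efficacy data. If the finding is judged a major deviation affecting efficacy, she would be lost from the per-protocol set. With about 10 to 14 women per arm, the secondary comparisons of hot flash frequency, severity and severity score have little room to absorb either outcome.

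**Working it through.** This is a check of timing, so the main step sets the schedule side by side.

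| Step | Where stated | Thyroid result available? |
|---|---|---|
| Eligibility review at Screening | Section 7.1, Table 1 | No: no thyroid test listed |
| Eligibility confirmation on Day -1 | Section 7.2, Table 1 | No: no thyroid test listed |
| Re-check of key criteria | Table 1, footnote 2 | No: placed ahead of all other baseline assessments |
| Randomization | Table 1, footnote 5 | Not assured: allowed on Day -1, or on Day 1 before dosing |
| Thyroid draw, Day 1 predose | Section 7.4, Table 1 footnote 14 | Sample taken; no step waits for the result |
| First dose | Section 7.4 | Not conditional on the result |

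Scheduled thyroid draws: Screening 0, Day -1 0, Day 1 predose 1, Day 14 1.

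Two readings needed care. Footnote 2 is attached to the Day 1 column as well as to Day -1. Even if the re-check is read as applying on Day 1, it comes before the other baseline assessments and so before the thyroid draw. Table 1 was also read from PDF and some columns may have shifted (serum pregnancy testing appears under Day 1 there but under Day -1 in Section 7.2). The point does not depend on the table, because Sections 7.1, 7.2, 7.4 and 7.7 give the same thyroid timing.

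**Size.** Section 12.1 gives 10 to 14 women per arm.

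- One woman as a share of an arm: 1/14 = 7.1% to 1/10 = 10%.
- If thyroid disease shifts her change in daily hot flashes by d, her arm mean moves by d/n, that is d/14 = 0.07d to d/10 = 0.10d.
- The expected number of affected women is p × N, with N from 40 to 56. The documents give no value for p. Assuming 1% to 5% purely to show scale, the range is 0.01 × 40 = 0.4 to 0.05 × 56 = 2.8 women in the trial. Divided over four arms, that is 0.1 to 0.7 per arm. The conclusion does not rest on this range.

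**The case against.** The best defence is that exclusion 9 is a clinical criterion, not a laboratory one. Where the protocol wants a test to decide entry, it names the test, limit or visit: creatinine, bilirubin, ALT/AST, FSH, virology, alcohol, drugs, COVID-19. Pheochromocytoma and carcinoid syndrome stand in the same exclusion without a screening assay, and the thyroid panel is assigned to an exploratory endpoint, for which a Day 1 baseline is suitable. This stands to the extent that the schedule does not contradict the criterion. It does not answer the practical point that the trial already runs a thyroid assay which could inform the criterion, and runs it too late to do so.

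Several stronger readings are tempting, and the documents do not support them:

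- **That nobody with thyroid disease can be excluded.** Known disease can be found through medical history at Screening and Day -1, the medication record and review (Sections 5.3.2 and 11.3.3), the physical examination, or exclusion 16. Only unrecognised disease escapes, although the body systems listed for history in Section 11.3.1 omit endocrine.
- **That an abnormal Day 1 result has no consequence.** Under Section 11.3.7, clinically significant abnormalities are recorded as adverse events, repeated and followed. Section 5.4 lets the investigator withdraw a subject. What is missing is an eligibility consequence.
- **That a result before dosing is impossible.** Section 11.3.7 has tests run at the clinical unit, randomization may wait until Day 1, and exclusion 16 has no time window. The protocol gives no turnaround time, and no step requires the result before dosing.
- **That the treatment comparison would be biased.** Allocation is randomized, so affected women add noise or chance imbalance.
- **That such women would not respond to the drug, or would distort the thyroid endpoints.** The documents contain nothing on response in thyroid disease, and the hormone endpoints are changes from each woman's own baseline.

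**Conclusion.** The point holds as a gap between a criterion and the schedule. No scheduled eligibility step uses a thyroid result, so unrecognised hypothyroidism or hyperthyroidism can enter the trial even though the protocol names both as confounding the symptom being measured.

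The consequence is modest. Each affected woman is 7% to 10% of an arm, but the number of such women cannot be estimated from the documents, and no effect on an endpoint can be calculated without assuming both the prevalence and the shift d. The primary objectives are pharmacokinetics and safety; efficacy is secondary and described as preliminary. This is a cheap improvement to the screening schedule, not a threat to the trial's validity. The conclusion assumes only that the visit lists in Section 7 are complete as to which thyroid tests are done and when.

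**What to change.** Add TSH, with reflex free T4, to the Screening blood draw in Section 7.1, Table 1 and Table 5, and label it an eligibility test as is done for FSH. Exclusion 9 can then draw on the result, and exclusion 14 reaches it because it is a Screening value. No new numerical limit is needed: exclusion 14 already relies on a judgement of clinical significance. Table 1 footnote 13, which lists what is repeated when Screening runs past 28 days, should say whether TSH is included. Keep the Day 1 and Day 14 samples as baseline and endpoint.

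The cost is one assay per woman screened, on blood already being drawn, including for those who fail screening on other grounds, and possibly a few more screen failures.

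If the sponsor prefers not to add the test, the protocol should at least say that exclusion 9 is applied by history and clinical judgement alone, and how a woman with an abnormal Day 1 thyroid result is handled in the modified intent-to-treat and per-protocol sets.
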